The economic impact of POAF on hospital resources is staggering. POAF lengthens hospital stay an average of two to four days costing the health care system an estimated 2 billion dollars per year (1,3). Additionally, there are associated costs and morbidity such as bradydysrhythmias, hypotension,

bleeding, and the utilization of antiarrhythmic and anticoagulant drugs in the treatment of POAF. The most severe complication of POAF is stroke and patients permanently debilitated by a stroke are known to have a decreased life expectancy (4,9).

Ninety percent of thrombi resulting from AF are found in the left atrial appendage (LAA) and are thus the source of embolic stroke due to AF (20). Post open heart surgery patients who experience POAF are at nearly a 20% risk for long term AF with all its adverse sequela including heart failure and decreased survival (22).

Although multiple causes for POAF have been examined such as inflammatory mediators, autonomic innervation, or surgical trauma, one definitive etiology has not been found (1,25). What is known is that the etiologic cause stimulates firing of the most common (90%) triggers of AF which are electrical impulses originating in the pulmonary veins (10). The procedure to eliminate these drivers of spontaneous electrical activity causing AF is known as ablation. Ablation can be done in the cardiac catheterization lab or the operating room. Different energy sources such as cryotherapy, radiofrequency, or high intensity ultrasound, may be used depending on operator preference. Whether performed surgically or percutaneously the cornerstone of ablative therapy relies on pulmonary vein isolation (35,36). Ablation has been proven to be more effective than medical therapy regardless as to the context in which AF occurs (35,36).

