European Society of Cardiology conclusively demonstrated that surgical occlusion of the LAA markedly decreased the risk of stroke in comparison to controls: at 3.7 years 6% in patients with no LAA versus 18% in the control population(42).

[figure not shown]

Figure 2. Pulmonary vein isolation procedure

Hypothesis

We hypothesize that performing a prophylactic limited left sided surgical maze, i.e., pulmonary vein isolation and excision of the left atrial appendage, in a group of at risk cardiac surgical patients at the time of the index procedure, will reduce the incidence of POAF. The null hypothesis is that the prophylactic surgical ablation will have no effect on the incidence of POAF.

Setting of the Research

This study will be conducted at a single center, Spectrum Health. The PI and all Spectrum Health cardiothoracic surgeons participating in the study are highly qualified and certified by the American Board of Thoracic Surgery. They are all proficient in performing the maze procedure as it is commonly utilized in everyday practice to manage and treat AF.

Subjects will be seen in the cardiothoracic surgeon's office and/or the hospital inpatient setting. The surgery will be performed at the Meijer Heart Center, Spectrum Health Hospitals.

Resources Available to Conduct this Research

Spectrum Health cardiothoracic surgeons perform approximately 1200 heart surgeries per year. Approximately 300 of these surgeries which include isolated coronary artery bypass grafting (CABG), isolated aortic valve replacement (AVR), or combined AVR/CABG are performed in patients ≥ 70 years of age. Therefore, we do not anticipate difficulty recruiting the necessary number of subjects during the enrollment period.

The PI will have dedicated research time in his schedule. Experienced research staff from the CV Structural Heart Team will assist with the study as delegated by the PI.

Study Design

This is a single-center, prospective, randomized, unblinded, interventional feasibility study to determine whether or not a prophylactic limited left sided surgical maze procedure is effective in reducing or preventing POAF. A high risk population with no history of atrial fibrillation or flutter, with a baseline risk of POAF of 40% or greater will be chosen. This includes CABG/AVR, isolated AVR, and isolated CABG patients 70 years and older. Up to 60 subjects who are scheduled to undergo elective open heart surgery will be randomized 1:1 into one of two study arms:

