- 1. Control arm: Elective open heart surgery without a limited left sided maze procedure.
- 2. Treatment arm: Elective open heart surgery with a limited left-sided maze procedure.

Sample Size Determination

No sample size calculation was performed as this is a feasibility trial and the number is fixed at 60 patients where 30 will be randomly assigned to the control arm and 30 randomly assigned to the treatment arm.

Statistical Methods

Summary statistics will be calculated. Quantitative variables will be expressed as mean ± standard deviation or median [interquartile range]. Qualitative variables will be expressed as frequency (percent). To determine if there is an association in POAF and the two arms of the study, a Chi-Square Test or Fishers Exact test will be used depending on assumptions being met. To look at our secondary outcomes such as hospital length of stay and incidence of postoperative reoperations for bleeding, a two sample t-test or Wilcoxon Rank Sum will be used to determine if there is a difference between the two groups and those that had POAF vs. those that didn't. Significance will be assessed at the 0.10 level. A level of 0.10 will provide more power to the study while only allowing a slight increase in error.

Recruitment methods

All subjects who receive an inpatient or outpatient heart surgery consult and meet the criteria may be approached about study participation. Consults will occur in the Cardiothoracic Surgeon's office of the Meijer Heart Center or Spectrum Health inpatient units. The subject's electronic medical records (EMR), Cerner and Epic, will be reviewed. There are no plans for advertisement or patient payment related to study participation.

It is expected enrollment will take approximately 6 months.

Inclusion and Exclusion criteria

Inclusion Criteria

- 1. Male or female
- 2. Age \geq 70 years
- 3. Elective cardiac surgery: isolated AVR, isolated CABG, or AVR/CABG,

Exclusion Criteria

- 1. A history of AF or atrial flutter
- 2. Less common cardiac operations such as aortic root replacements, aortic dissections, myxoma excisions, or pericardectomies. Beating heart or off-pump procedures, redo open heart procedures.
- 3. Subjects with existing pacemaker and/or AICD
- 4. Vulnerable populations; adults unable to sign consent, prisoners
- 5. Need for emergent or salvage surgery for any reason
- 6. Currently participating in an investigational drug or another device study (excluding registries)

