- 7. Subjects currently on antiarrhythmic drugs Class I and III including amiodarone.

Study endpoints

The incidence or absence of documented AF, defined by Society of Thoracic Surgeons (STS) registry data as the occurrence of POAF or atrial flutter that requires treatment, is the primary endpoint (21). In addition, length of stay (LOS) and additional antiarrhythmic or anticoagulant medications will be examined as a secondary endpoint.

Safety endpoints

The safety endpoint is the occurrence of one of the following events between time of procedure and the 30 day post procedure assessment:

- All-cause death
- TIA/stroke
- Bleeding (chest tube drainage) that is procedure related and requires take back to the operating room or blood transfusions
- Incidence of AF
- Need for permanent pacemaker
- Evidence of pulmonary vein stenosis defined as > 50 % occlusion of the vessel.

Procedures Involved in the Research

Baseline preoperative cardiac surgery workup will be done on all patients according to standard of care. This workup will consist of:

- History and physical exam
- Chest X-Ray

- Electrocardiogram
- Echocardiogram
- Cardiac catheterization
- Blood and urine tests such as complete blood count, complete metabolic count, cardiac enzymes, type and screen, and urinalysis. Any other indicated tests based on patient history and index procedure i.e.; pulmonary function tests, carotid ultrasound, leg vein mapping, noncontrast chest CT.

Prior to enrollment, the protocol and informed consent must be approved by the Spectrum Health Institutional Review Board (IRB). IRB approved Health Insurance Portability and Accountability Act (HIPPA) will also be used. A regulatory binder and subject binders will be created according to local requirements and stored in the CV Research Department.

Before the subject signs the informed consent form (ICF), the investigator or designated study personnel will explain the research, study procedure, anticipated benefits, and potential risks of study participation. Adequate time will be allowed to read the ICF and ask questions. The original signed ICF will be kept with the subject's research records and a copy will be given to the subject.

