Postoperative monitoring, diagnostic and lab tests will be done according to Spectrum Health standard of care. Current standard of care for the postoperative cardiac surgery patient at this institution consists of continuous telemetry monitoring, collection of arterial blood gases, complete blood count, basic metabolic panel and blood glucose at regular intervals. An EKG is obtained on arrival to the recovery area and any time a cardiac dysrhythmia is noted.

In addition to standard of care, subjects who were randomized to the treatment arm of the study will have a pre-discharge transthoracic echocardiogram to assess the absence or presence of thrombus in the left atrium. If thrombi are noted, subjects will be anticoagulated per standard of care.

The highest risk of POAF is within the first 48 to 96 hours after surgery. All post-operative patients are on continuous 24 hour telemetry after surgery until hospital discharge. While it depends on the index procedure that was done, the usual length of stay at this institution following elective cardiac surgery is 5 to 7 days.

If subjects develop POAF, paroxysmal or sustained, they will be treated with standard medications and protocols already in place for this complication.

The current protocol to treat POAF first entails escalation of beta blocker therapy if it is tolerated. If further treatment is necessary, patients are loaded with a dose of IV amiodarone and then changed to oral amiodarone for four weeks or longer if appropriate.

Our current standard of care at Spectrum Health for POAF anticoagulation is as follows. For POAF that persists for more than 24 hours or is episodic and occurs more than once, anticoagulation is initiated. Warfarin or one of the new oral anticoagulants such as dabigatran, rivaroxaban or apixiban will be used tailored to the individual patient utilizing their CHA2DS2-VASc score and surgeon preference.

In addition, all patients who receive a mechanical valve or a bio prosthetic mitral valve are started on an anticoagulant on postoperative day 2. The dose is titrated to an INR of 2.5-3.5.

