- Medications, pre- and post-op including name of medication, indication, dose.
- Procedure and date- including number of grafts and type of valve implanted
- CPB time, X-clamp time
- EKG rhythm(s), pre- and post-op (atrial flutter, SVT, VT, etc.)
- Post procedural stroke/TIA
- Post procedural MI
- Post procedural pacemaker implant
- Any bleeding complication
- Any incidents of POAF (date occurred, treatment used,)
- Length of stay

Data will also be collected at 6 weeks, 6 months and 12 months post-procedure. This will include:

- All adverse events
- Any rehospitalizations
- Medications, current and new
- Any episodes of AF or other cardiac arrhythmias
- EKG
- Need for pacemaker

• Echocardiogram: EF, valve gradients, left and right atrial function, pulmonary vein stenosis or presence of suspected thrombus.

In the event that we are unable to find subject information in the EMR at appointed study intervals, we may telephone subjects to inquire how they are and whether or not they have had any adverse events.

Assessments/procedures	Baseline	Hospitalization	Predischarge	Follow up	Follow up	Follow up
	Screening			6 weeks	6 months	12 months
				post	post	post
				procedure	procedure	procedure
				+/-7 days	+/- 7 days	+/- 7 days
Consent	Х					
History/Inclusion and	Х					
Exclusion						
Medication Review	Х	X		X	X	X
Randomization	Х					
AF occurrence and		X		X	X	X
treatment						
Transthoracic echo			X			
			Treatment			
			arm only			
Rehospitalizations				X	X	X
Adverse Events		X		X	X	Х

Adverse events

An adverse event (AE) is any untoward medical occurrence (signs, symptoms, abnormal laboratory findings) in a subject. It does not necessarily have to be caused by the device or procedure to be considered an adverse event.

A serious adverse event is one that led to death, serious deterioration in the health of the subject, resulted in a new hospitalization or prolonging the index hospitalization, a permanent impairment of a body structure or function, or required medical and/or surgical intervention to prevent further lifethreatening illness or injury

A device related adverse event is an event that in the investigators judgement may be related to the investigational device.

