There have been reports that amputation of the LAA may increase the risk of POAF but these are not consistent and a recent meta-analysis demonstrated no increased risk of POAF (43). Further a surgical Cox maze is always defined by management of the LAA either with amputation or creation of an epicardial surgical lesion at its base and occlusion of the LAA. Long term results of the maze procedure show no ill effects to the patient and left atrial transport function is maintained (30).

Globally the AtriCure device has been safely used in over 200,000 cases and is the predominant device used to perform surgical ablation of AF in the world. Thus the safety of the AtriCure device has been outstanding with almost no risk to the patient and the ablation lesions have no late or long-term adverse effects on the myocardium.

In a study published in Circulation of over 10,000 patients who underwent amputation of the LAA there was no increased risk of bleeding (16). Multiple large studies have demonstrated that a left sided or limited left sided surgical maze procedure adds no operative risk and only improves patient outcomes, especially in regard to long term stroke risk and survival (7,8,17,28,29,44). A recent 2018 publication from the STS Adult Cardiac Database strongly corroborates LAA removal as it markedly decreased the long term risk of stroke (42).

The strongest evidence, that there is no additional risk to the patient, is put forth in the 2017 Guidelines for The Surgical Treatment of Atrial Fibrillation set by The Society of Thoracic Surgeons: "Surgical ablation for AF can be performed without additional operative risk, and is recommended at the time of concomitant isolated AVR, isolated CABG and AVR+CABG operations to restore sinus rhythm." The Society of Thoracic Surgeons labels this as a Class I recommendation; meaning that the procedure should be performed as a standard of practice because it is useful, effective, and the benefits far outweigh the risks.

A recent Russian study examining the effects of prophylactic pulmonary vein isolation with radiofrequency ablation in patients undergoing isolated CABG has shown very promising results. The incidence of POAF was reduced by 21% versus controls and at one year the effect was sustained as 98% of the prophylactic group was free from AF versus 84% of the controls. The conclusion was "simultaneous preventive pulmonary vein isolation during CABG is safe and effective" (40).

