Application will be made to CMS for reimbursement consideration. Subject's health insurance will be billed for costs that are part of usual medical care. Any co-payment, co-insurance or deductible, will be the responsibility of the subject. There are no extra costs to subjects for participating in this research study. The pre-discharge transthoracic echocardiogram required for the study (treatment arm only) will not be billed to the subject or their insurance.

Consent Process

Once a subject has been identified as meeting criteria for the study, the PI and/or other delegated study personnel will explain the study in detail to the subject. This discussion will take place in privacy at Spectrum Health. Adequate time will be allowed for questions. A copy of the consent will be given to the subject to read and review. After allowing the subject adequate time to review the consent, the research coordinator will answer any additional questions and ensure that the subject realizes participation is voluntary. A signed copy of the informed consent will be given to the subject.

Sharing of Results with Subjects

There are no plans to share research results with subjects.

References

- 3. Atrial Fibrillation After Cardiac Surgery ed. Jonathan Steinburg 2007 Springer Science & Business Media

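### Does a study echocardiogram done before discharge in the treatment arm only distort the length-of-stay comparison?

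*Combined protocol and SAP*

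**What the plan says.** - **The echo.** Procedures Involved in the Research states that "subjects who were randomized to the treatment arm of the study will have a pre-discharge transthoracic echocardiogram". Its purpose is to detect thrombus in the left atrium, and a positive finding leads to anticoagulation under usual practice. Cost to Subjects confirms that it is a research test, not billed to the patient or insurer. In the schedule table under Data management, "Transthoracic echo" is the only entry in the predischarge column and is marked for the treatment arm alone. No day or window is attached to that column.
- **The endpoint.** Study endpoints says that "length of stay (LOS) and additional antiarrhythmic or anticoagulant medications will be examined as a secondary endpoint". Statistical Methods says that for outcomes such as "hospital length of stay and incidence of postoperative reoperations for bleeding, a two sample t-test or Wilcoxon Rank Sum will be used", both between arms and by POAF status.
- **The data.** Data management lists echo measurements, procedure date, LOS, and medications with their indication. It names no echo date and no date of readiness for discharge. The list is introduced as what the data will include. The text just before it has research staff visiting each patient daily and reviewing the electronic record.

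**The concern.** A test that must precede discharge and exists in one arm only can lengthen the stay in that arm. If a patient is fit to leave but the echo is still outstanding, the extra day counts as LOS. Patients know their assignment and the study is unblinded, so nothing equalises this between arms. Saving bed days is one of the stated reasons for the procedure: Background says "POAF lengthens hospital stay an average of two to four days". A systematic delay would be subtracted directly from any gain, and more patients would not remove it. A feasibility study may pass its LOS estimate to a later trial, so a hidden delay could make a useful procedure look neutral.

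A smaller form of the same worry concerns the medication endpoint. A thrombus found by this echo leads to anticoagulation, and nobody looks for thrombus in controls. If anticoagulants for any indication were counted, that would be a one-arm route to the endpoint.

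**Working it through.** The plan gives no LOS effect, no LOS standard deviation and no power calculation (the sample size is fixed at 60), so there is no figure of its own to reproduce. The check sets the possible size of a delay against the expected gain and the sampling error.

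**Inputs from the protocol.** Extra stay per POAF case: 2 to 4 days (Background). Baseline: a population "with a baseline risk of POAF of 40% or greater will be chosen" (Study Design). Effect in one cited study of pulmonary vein isolation at isolated CABG: "The incidence of POAF was reduced by 21% versus controls" (Risks/Benefits to Subjects), without saying whether that is absolute or relative. Arm size: 30. Usual stay: 5 to 7 days.

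**Assumptions.** The share *w* of treated patients who wait one day (0, 10, 25 or 50%), and an LOS standard deviation of 2 to 3 days. The protocol gives neither.

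**Expected gain** = reduction in POAF risk × extra days per case.
- 21 points absolute: 0.21 × 2 = 0.42 to 0.21 × 4 = 0.84 days.
- 21% relative to 40%: 0.21 × 0.40 = 0.084, giving 0.084 × 2 = 0.17 to 0.084 × 4 = 0.34 days.
- POAF eliminated from 40%: 0.40 × 2 = 0.8 to 0.40 × 4 = 1.6 days.

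**Gain left after the delay** = gain − *w* × 1 day.

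| *w* | Relative 21% | Absolute 21 points | Elimination |
|---|---|---|---|
| 0 | 0.17 to 0.34 | 0.42 to 0.84 | 0.80 to 1.60 |
| 10% | 0.07 to 0.24 | 0.32 to 0.74 | 0.70 to 1.50 |
| 25% | −0.08 to 0.09 | 0.17 to 0.59 | 0.55 to 1.35 |
| 50% | −0.33 to −0.16 | −0.08 to 0.34 | 0.30 to 1.10 |

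At *w* = 25% the loss is 0.25/0.84 = 30% to 0.25/0.42 = 60% of the gain on the absolute reading, and 0.25/1.6 = 16% to 0.25/0.8 = 31% under elimination. To cancel the gain completely, a one-day wait would be needed in 42 to 84% of treated patients on the absolute reading (12.6 to 25.2 of 30), or 17 to 34% on the relative reading (5.0 to 10.1 of 30).

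**Sampling error.** SE = SD × √(2/30): 2 × 0.258 = 0.52 days and 3 × 0.258 = 0.77 days. A two-sided 0.10 test of a 0.84-day gain at SD 2 has power 0.49 with no wait and 0.31 with *w* = 25%. At SD 3 the no-wait power is already only 0.29.

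**Does the text imply a wait?** No. The word used for the echo's timing sets a latest point, not a hold on discharge. A separate schedule column shows only that the test comes before the patient leaves. With a stay of 5 to 7 days there are several days in which to do it. Every row of the table below the first is therefore hypothetical.

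**Medication endpoint.** One detected thrombus in a patient not otherwise anticoagulated moves the arm by 1/30 = 3.3 points. The protocol knows of no thrombus from isolated epicardial pulmonary vein lesions, so the expected number is near zero. Indication is recorded, so AF-related use can be separated.

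**The case for a change.** The strongest reply is that noise and bias are different things. A delay confined to one arm has one direction and does not shrink with sample size, and on the relative reading of the 21% a modest delay takes most or all of the gain. The protocol sets no echo day, and a reason for late discharge is harder to recover afterwards than a date. Naming the day and adding date fields would cost almost nothing.

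The direction and the missing detail stand. Three things weaken the rest.

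- The delay itself is supposed, not found in the text.
- It could probably be seen if it occurred. The data list is open-ended, staff see patients daily, and the hospital record should hold echo and discharge dates. Only a formal date of readiness for discharge is clearly not planned.
- A sensitivity analysis that removes waiting days would rest on unblinded staff judging when a treated patient was ready to leave, and it could only shorten LOS in the treatment arm. That exchanges a hypothetical bias against the procedure for a possible one in its favour.

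Nor does the asymmetry call for removing the echo or adding it in controls: it is a safety check for a possible consequence of a procedure that controls do not have.

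**Conclusion.** The observation is accurate but does not call for a change. The one-arm echo is a fair safety trade-off, and its unstated day is a gap that ordinary conduct fills: the test is done during the stay, and its date can be read from the record if anyone doubts the LOS result. Followed as written, the plan is not shown to give a wrong LOS comparison.

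The bias is zero if the echo fits within the usual stay. It is 0.25 days against the procedure if a quarter of treated patients wait one day, which is below the standard error of 0.52 to 0.77 days. These figures rest on the assumed wait and the assumed SD. The share of the gain at risk depends heavily on which POAF reduction is used, since the 21% comes from one cited study and is not a planning value of this trial. LOS is a secondary outcome in a 60-patient feasibility study with no powered comparison. The primary POAF endpoint could be touched only through a little extra telemetry time, after the 48 to 96 hours that the protocol names as the peak risk period.
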